### **8.3 RUD Lite**

The RUD Lite assesses both formal and informal resource use, making it possible to calculate costs from a societal perspective. The RUD Lite is administered as an interview with the caregiver. The following dimensions are captured on the subject’s part: accommodation/long term care, respite care, hospital care, social service, home nursing care, and work status. In addition, the following aspects are covered from the caregiver perspective: caregiving time for the subject and work status.

Each component of caregiver time will be calculated as the hours of care on a typical day multiplied by days spent on providing these services and summarized descriptively by visit. Caregiver work status, whether the subject was admitted to a hospital, whether the subject received services in a hospital emergency room, whether the subject visited any health care professional, whether the subject received any nursing services as well as caregiver relationship with subject and the subject’s living accommodations will also be summarized descriptively by visit.

The RUD Lite unit cost and economic modelling, and additional sensitivity analyses will be addressed in a separate external SAP.

## **9. CHANGES TO PROTOCOL-SPECIFIED ANALYSES**

Any changes will be documented in the Clinical Study Report in Section 9.8.

**APPENDICES**

**Appendix A: Post-Dose Visit Windows**

Visit windows are defined in the following table. Unscheduled and early termination visits are included in the windowing algorithm.

Target Visit	Visit Window Time Interval (Study Day*)	Scheduled Day
Baseline	< 2	NA
Week 2	2 to 53	15
Week 13	54 to 137	92
Week 26	138 to 228	183
Week 39	229 to 319	274
Week 52	320 to 410	365
Week 65	411 to 501	456
Week 78	502 to 591	546
Week 91	592 to 683	637
Week 104	> 683	729
Follow-up	First post-treatment value at least 14 days after last dose	

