#### **4.4 Visit Windows**

Since study visits do not always take place exactly as scheduled in the protocol, it is necessary to assign the actual observation times to “analysis visit windows” for analysis purposes. Post-baseline visit windows for each target visit are defined in [Appendix A](#), and will be applied to all measurements. For each summary and value if there are multiple values within a visit window, the “worst” value as defined in [Appendix D](#) will be used for that visit window summary. These visit windows will be applied to all visits, including scheduled, unscheduled, and early termination visits.

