## 7.2 Clinical Laboratory Evaluation

Central laboratory data are transferred electronically by Covance. The Data Transfer Specification document provides a detailed description of the content and format of the laboratory datasets. Both conventional and SI units are provided and will be summarized in separate tables and listings. The eGFR values will be calculated and included in the tables and listings for clinical chemistry parameters.

Results from local laboratories are entered into the CRF by the site; these will not be included in summary tabulations but will be included in the data listings together with the corresponding normal ranges. Values for local laboratory parameters will be converted to the corresponding alternative units, either conventional or SI, depending on how reported.

For the summary tabulations of laboratory results, Baseline is defined as the last non-missing value prior to first dose of study drug in 020. Laboratory tests obtained on the date of the first dose will be assigned to pre-treatment. For each analyte, Baseline values will be restricted to those subjects in the safety population for whom there is at least one post-Baseline value (either overall or for the corresponding target visit). Any lab result 14 or more days after the last dose will be considered post-treatment.

Visit windows are used when results are presented by target visit (see [Appendix A](#)). For each analyte, if a subject has multiple values within a visit window, the “worst” value as defined in [Appendix D](#) will be used for that visit window summary.

Results of all continuous laboratory parameters will be summarized using descriptive statistics at baseline and at each post-baseline target visit; the last available on-treatment value and post-treatment results will also be summarized. The baseline data may come from the prior study, if not repeated in 020. For each subsequent target visit, changes from baseline will also be summarized by the number and percentage of subjects and the mean, median, SD, minimum, and maximum values for continuous laboratory parameters. These will also be prepared for subjects categorized by diagnosis and AChEI/Memantine use.

Box and whisker plots will be presented for selected parameters including hemoglobin, reticulocytes (%), neutrophils, and liver function tests. Other parameters may be identified during data review.

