#### **7.5 Electrocardiography**

A 12-lead ECG (triplicate recording) was introduced in protocol version 3.0. Measurements are taken approximately every 6 months thereafter (or upon early termination), including the 4-week post-treatment follow-up visit if applicable. Recordings will be evaluated by a centralized ECG reading facility. Interval data (including QT and corrected QT intervals), ventricular rate, and overall interpretation are to be reported for every ECG. The interval data and ventricular rate are to be noted in the CRF as averages of the three readings (with the exception of values that are not evaluable and reported as zero, in which case the average will exclude this zero value and note in the CRF the average of values > 0).

ECG interval and ventricular rate data will be summarized using descriptive statistics. Windows for each target visit will be used ([Appendix A](#)). Parameters to be analyzed include heart rate (HR) and PR, QRS, QT, and corrected QT (using Fridericia's and Bazett's corrections), and RR intervals. Counts and percent of subjects in each result

category will be tabulated. Overall interpretations of abnormalities will also be tabulated, with subjects categorized by whether or not they have study-emergent abnormalities.

Subjects are also to be categorized and enumerated on the basis of QTcB/F interval as follows:

- Absolute measurements (in categories of  $> 450$  to  $\leq 480$ ,  $> 480$  to  $\leq 500$ ,  $> 500$  msec)
- Change from first 020 measurement (in categories of  $> 30$  to  $\leq 60$ ,  $> 60$  to  $< 90$ ,  $\geq 90$  msec)

All HR, interval data, and interpretations will be listed. Any local ECG results (optional prior to version 3.0 of the protocol) will be listed separately.

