**Appendix D: Rules for Determining “Worst” Value**

**“Worst” Clinical Laboratory Value**

Rule	Parameters
Highest value	Hematology: eosinophils, basophils, monocytes, reticulocytes
	Serum chemistry: ALT, AST, ALK-P, creatinine, total bilirubin, urea (nitrogen), uric acid, LDH, creatine kinase, GGT
Lowest value	Hematology: neutrophils, RBC count, HCT, hemoglobin, platelets
	Serum chemistry: albumin, creatinine clearance total protein
Farthest from normal range midpoint	Hematology: WBC count, lymphocytes, MCV, MCH, MCHC
	Serum chemistry: glucose (random), Na, K, phosphate, calcium, chloride

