**“Worst” ECG Measurement**

Parameter	Criterion for “Worst” ECG
PR	Highest
QT (QTcF and QTcB)	Highest
QRS	Value farthest from midpoint of normal range
Heart Rate	Value farthest from midpoint of normal range

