**Table 14.3.3.1.1.1**  
**Hematology Values and Changes from Baseline at All Visits – Conventional Units**  
**Safety Population**

Laboratory Parameter	Target Visit	AD (N= )	bvFTD (N= )	All Subjects (N= )
Hematocrit (%)	Baseline 			
	n	n	n	n
	Mean (SD)	xx.x (xx.xx)	xx.x (xx.xx)	xx.x (xx.xx)
	Median	xx.x	xx.x	xx.x
	Min, Max	xx, xx	xx, xx	xx, xx
	By-visit Baseline for Week 2 Visit 			
	N	n	n	n
	Mean (SD)	xx.x (xx.xx)	xx.x (xx.xx)	xx.x (xx.xx)
	Median	xx.x	xx.x	xx.x
	Min, Max	xx, xx	xx, xx	xx, xx
	Week 2			
	N	n	n	n
	Mean (SD)	xx.x (xx.xx)	xx.x (xx.xx)	xx.x (xx.xx)
	Median	xx.x	xx.x	xx.x
	Min, Max	xx, xx	xx, xx	xx, xx
	Change from Baseline to Week 2			
n	n	n	n	
Mean (SD)	xx.x (xx.xx)	xx.x (xx.xx)	xx.x (xx.xx)	
Median	xx.x	xx.x	xx.x	
Min, Max	xx, xx	xx, xx	xx, xx	
...				
Hemoglobin (g/dL)				
.				
.				

 Baseline is defined as the last non-missing value prior to first dose of study drug.

 By-visit Baseline is defined as the baseline assessments from subjects with a non-missing assessment at that visit.

path\t\_program.sas date time

*Programming note: Table will include all hematology parameters collected from Central Laboratory, and all target visits and for Last Available On-Treatment Value. Please see Appendix A for visit windows.*

*Programming Note: Repeat table for the tables listed below*

*Table 14.3.3.1.1.2 Hematology Values and Changes from Baseline at All Visits – Conventional Units – Non-AChEI/Memantine Users (Safety Population)*

- Table 14.3.3.1.2.1 Hematology Values and Changes from Baseline at All Visits – SI Units (Safety Population)*
- Table 14.3.3.1.2.2 Hematology Values and Changes from Baseline at All Visits – SI Units – Non-AChEI/Memantine Users (Safety Population)*

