**Table 14.3.3.3.1**  
**Incidence of Potentially Clinically Significant Hematology and Serum Biochemistry Results**  
**Safety Population**

Laboratory Parameter	Potentially Clinically Significant Criteria	Target Visit	AD m/n (%)  (N= )	bvFTD m/n (%)  (N= )	All Subjects m/n (%)  (N= )
Hematology					
Hemoglobin	Criteria	Baseline	m/n (%)	m/n (%)	m/n (%)
		Any Post-Baseline PCS	m/n (%)	m/n (%)	m/n (%)
		Any Post-Baseline Worsening	m/n (%)	m/n (%)	m/n (%)
		Week 2	m/n (%)	m/n (%)	m/n (%)
		Week 13	m/n (%)	m/n (%)	m/n (%)
Serum Chemistry					
Sodium	Criteria	Baseline	m/n (%)	m/n (%)	m/n (%)
		Any Post-Baseline PCS	m/n (%)	m/n (%)	m/n (%)
		Any Post-Baseline Worsening	m/n (%)	m/n (%)	m/n (%)
		Week 2	m/n (%)	m/n (%)	m/n (%)
		Week 13	m/n (%)	m/n (%)	m/n (%)

Note: ULN = Upper Limit of Normal.

 m: number of subjects with at least one potentially clinically significant result at corresponding visit; n: number of subjects with at least one non-missing result at corresponding visit.

Note: For the post-Baseline visits, only subjects in whom the values represent a treatment-emergent worsening from Baseline (i.e. more out of range) are summarized.

path\t\_program.sas date time

*Programming note: Table will include all parameters with defined potentially clinically significant ranges at each post-Baseline visit and for Last Available On-Treatment Value. Please see Appendix A for target visits and visit windows. Ensure that criteria indicating an increase or a decrease are presented separately.*

*Programming Note: Repeat table for Table 14.3.3.3.2 Incidence of Potentially Clinically Significant Hematology and Serum Biochemistry Results – Non-AChEI/Memantine Users (Safety Population)*

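### The Week 104 analysis window has no upper limit, so its by-visit safety rows take the worst of every later on-treatment visit

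*SAP*

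**What the plan says.** SAP Appendix A gives each target visit from Week 2 to Week 91 a closed range of study days. The final on-treatment row reads "Week 104 > 683 729": it starts after Day 683, is scheduled for Day 729 and has no end. The only row after it, Follow-up, takes post-treatment values only.

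SAP 4.4 applies these windows to all measurements from scheduled, unscheduled and early termination visits. Its rule for repeats begins "For each summary and value if there are multiple values within a visit window" and takes the Appendix D worst value. SAP 7.2 repeats this for laboratory data ("For each analyte, if a subject has multiple values within a visit window"), and SAP 7.3 does so for vital signs. For ECGs, SAP 7.5 says "Windows for each target visit will be used", and Appendix D has its own worst-ECG table. Under Appendix D the lowest value is taken for "Hematology: neutrophils, RBC count, HCT, hemoglobin, platelets" and the highest for PR, QT and QTc.

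Treatment past Week 104 is provided for. Protocol 4.3 sets no fixed end. Note b to Protocol Table 4-1 offers continuation at Visit 6, Visit 10 and so on; Visit 10 is Week 104. Protocol 4.4 keeps the 13-week and 26-week schedules after the first year. SAP Listing 16.2.1.1.3 takes the decision to continue from the Visit 6 and Visit 10 CRFs.

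**The concern.** An on-treatment value collected after Week 104 has nowhere to go but the Week 104 row. A subject who stays in the study contributes two, three, four or more scheduled visits to that row, and the worst-value rule selects the most extreme. Baseline is a single last pre-dose value, so the selection does not cancel in the change from baseline.

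The outputs affected are the by-visit means and changes, the last box in the laboratory box plots, the by-visit counts of potentially clinically significant (PCS) values and the by-visit QTc categories. Long-term safety is a primary objective, and this is the row where a reader looks for late toxicity. A stable population could appear to show falling hemoglobin or lengthening QTcF there, under a label of the same form as the single-visit rows. A real change could not be dated to Week 104, 117 or later.

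**Working it through.** **The plan's own limits.** The scheduled days in Appendix A are 15, 92, 183, 274, 365, 456, 546, 637 and 729. Midpoints of neighbouring days are 53.5, 137.5, 228.5, 319.5, 410.5, 501, 591.5 and 683. Rounded down, these give 53, 137, 228, 319, 410, 501, 591 and 683, which are all eight stated upper limits. The SAP does not state a midpoint rule, but its table follows one.

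**Where Week 104 would end.** With 13-week visits and scheduled day = 7 × week + 1, the days after 729 are 820, 911, 1002 and 1093. The midpoint (729 + 820)/2 = 774.5 gives Day 774. The next limits are 865, 956 and 1047. With the protocol's ±14 days, the Week 104 visit falls on Days 715–743 and Week 117 on Days 806–834, so Day 774 separates them.

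**Scheduled visits in the open window (k).** For laboratory tests and vital signs, k = 1 at Week 104, 2 at Week 117, 3 at Week 130 and 4 at Week 143. ECGs are 26-weekly, so k = 2 is reached at Week 130 (Day 911).

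**Shift with no true change, highest- or lowest-value parameters.** Assume exchangeable normal values with between-visit correlation ρ = 0.7 (not in the documents). The shift in within-subject SDs is E[max of k standard normals]. In total SDs it is multiplied by √(1 − 0.7) = 0.548. In SDs of the change from baseline it is divided by √2.

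| k | Within-subject SD | Total SD | SD of change |
|---|---|---|---|
| 2 | 0.564 | 0.309 | 0.399 |
| 3 | 0.846 | 0.464 | 0.598 |
| 4 | 1.029 | 0.564 | 0.728 |

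**Effect on the row mean.** This is the shift multiplied by the share who stay. At k = 4 and shares of 10%, 25%, 50% and 75%: 0.564 × 0.10, 0.25, 0.50, 0.75 = 0.06, 0.14, 0.28 and 0.42 total SD. A 0.1 total-SD shift needs a share of 0.1/0.309 = 32% (k = 2), 0.1/0.464 = 22% (k = 3) or 0.1/0.564 = 18% (k = 4).

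**PCS counts.** SAP Table 14.3.3.3.1 defines its numerator as "m: number of subjects with at least one potentially clinically significant result at corresponding visit". Take an assumed 2% rate per visit. If visits are independent, the rate for a subject is 1 − 0.98^k; the ρ = 0.7 figures are from the same normal model.

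| k | ρ = 0.7 | Independent |
|---|---|---|
| 2 | 3.4% | 4.0% |
| 3 | 4.4% | 5.9% |
| 4 | 5.3% | 7.8% |

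For the row at k = 4, rate = (1 − share) × 2% + share × 5.33% (or 7.76%). This gives 2.3–2.6% if 10% stay, 2.8–3.4% if 25% stay and 3.7–4.9% if 50% stay.

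**Farthest-from-midpoint parameters.** If values are centred on the midpoint, the mean does not move but the spread grows. In 1,000,000 simulated subjects, the SD for those who stay is multiplied by 1.32 (ρ = 0.7) to 1.45 (independent) at k = 3, and by 1.40 to 1.57 at k = 4.

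**The case against.** Five points can fairly be made for the plan.

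- **Day 774 is only an inferred cut.** The next scheduled laboratory visit is no earlier than Day 806, and the next scheduled ECG no earlier than Day 911 − 14 = 897. This is right for scheduled visits. However, a subject who stops after Day 774 should have an early termination visit, with ECG, that enters the same window.
- **The rule is the same in every row; only the width differs.** Formally so, and the PCS table does say it counts at least one result. But the Week 26 to Week 91 windows are 90 to 92 days wide and hold one scheduled visit, whereas the last window can hold any number.
- **Nothing shows that subjects pass Week 104.** The Visit 10 form shows only that the question is asked, and if nobody stays the effect is nil. This stands: the size is unknown, although the plan expressly allows for it.
- **The row-level figures assume that all who stay reach k = 4.** If they are spread evenly over k = 2, 3 and 4, the shift per such subject is (0.309 + 0.464 + 0.564)/3 = 0.446 total SD. The row then moves 0.11 or 0.22 if 25% or 50% stay, rather than 0.14 or 0.28. This is a fair reduction.
- **Other outputs limit the harm.** The laboratory tables cover "and all target visits and for Last Available On-Treatment Value", and that last-value row is sound. Any-post-baseline PCS counts, adverse event tables, dated listings, the MMSE mixed model and Follow-up values are untouched, and the safety summaries are descriptive. All true, but none of it corrects the Week 104 row.

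The open category for late discontinuations in SAP 5.2 is harmless, because each subject is counted once and no worst value is taken.

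**Conclusion.** The concern holds. Followed as written, the plan produces a final target-visit row that is a worst-of-several value for anyone treated well past Week 104, set beside rows based on one scheduled visit and not labelled as different. That much rests on the documents alone.

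The size does not. The per-subject shifts in within-subject SDs need only normality, stable values and equal correlation between visits. The total-SD and PCS figures also rest on the assumed correlation (0.7, or independence for the upper PCS figure) and the assumed 2% rate. The effect on the row depends on the unknown share who stay and for how long. It should be corrected because it can imitate late toxicity in a long-term safety study, but it undermines no test and no adverse event result.

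**What to change.** Close Week 104 at Days 684–774 and continue the spacing already in Appendix A: Week 117 = Days 775–865, Week 130 = 866–956, Week 143 = 957–1047, and so on to the last observed visit.

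If one pooled late row is preferred, still close Week 104 at Day 774. Add a separate row for visits after Week 104, with a note that it is the worst of several visits and not comparable with the rows above. Relabelling the present row as Week 104 or later would not be enough, because the worst-of-several shift would remain in it.

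The cost is a longer window table and some sparse late rows, or a single extra row under the pooled option. If nobody stays past Day 774, no result changes.

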**Appendix B: Criteria for Determining Potentially Clinically Significant Values in Laboratory Test Results**

Test	Criteria	
	System International Units	Conventional Units
Hemoglobin	Female: $\leq 95$ g/L; Male: $\leq 115$ g/L Decrease of $\geq 20\%$	Female: $\leq 9.5$ g/dL; Male: $\leq 11.5$ g/dL
Hematocrit	Female: $\leq 0.32$ ; Male: $\leq 0.37$	Female: $\leq 32\%$ ; Male: $\leq 37\%$
WBC count	$\leq 2.8 \times 10^9/L$ $\geq 16 \times 10^9/L$	$\leq 2800/\mu L$ or $\geq 16000/\mu L$
Neutrophils	$\leq 1.0 \times 10^9/L$	$\leq 1000/\mu L$
Eosinophils	$\geq 0.7 \times 10^9/L$	$\geq 700/\mu L$
Platelet count	$\leq 75 \times 10^9/L$ $\geq 700 \times 10^9/L$	$\leq 75 \times 10^3/\mu L$ $\geq 700 \times 10^3/\mu L$
Sodium	$<130$ mmol/L $>150$ mmol/L	$<130$ mEq/L $>150$ mEq/L
Potassium	$< 3.0$ mmol/L $> 5.5$ mmol/L	$< 3.0$ mEq/L $> 5.5$ mEq/L
Calcium	$< 1.75$ mmol/L $> 3.00$ mmol/L	$< 7.00$ mg/dL $> 12.00$ mg/dL
Glucose, fasting/nonfasting/unknown	$< 2.775$ mmol/L $>13.875$ mmol/L	$< 50$ mg/dL $> 250$ mg/dL
Uric acid	Female: $>475.8$ $\mu\text{mol/L}$ ; Male: $>594.8$ $\mu\text{mol/L}$	Female: $> 8$ mg/dL; Male: $>10$ mg/dL
Albumin	$<25$ g/L	$<2.5$ g/dL
Total bilirubin	$\geq 34.2$ $\mu\text{mol/L}$	$\geq 2$ mg/dL
ALT	$\geq 3 \times \text{ULN}$	$\geq 3 \times \text{ULN}$
AST	$\geq 3 \times \text{ULN}$	$\geq 3 \times \text{ULN}$
Alkaline phosphatase	$\geq 3 \times \text{ULN}$	$\geq 3 \times \text{ULN}$
Urea (nitrogen)	$> 17.85$ mmol/L	$> 50$ mg/dL
Creatinine	$\geq 177$ $\mu\text{mol/L}$	$\geq 2$ mg/dL
CK	$\geq 3 \times \text{ULN}$	$\geq 3 \times \text{ULN}$
GGT	$\geq 3 \times \text{ULN}$	$\geq 3 \times \text{ULN}$
LDH	$\geq 3 \times \text{ULN}$	$\geq 3 \times \text{ULN}$
Phosphorus	$< 0.646$ mmol/L $> 1.777$ mmol/L	Low: $<2.0$ mg/dL High: $>5.5$ mg/dL

ULN = Upper Limit of Normal

**Appendix C: Criteria for Determining Potentially Clinically Significant Values in Vital Signs**

Test	Criteria
Systolic Blood Pressure (SBP) – Seated (mmHg)	Increase of $\geq 20$ mmHg from baseline and $\geq 180$ mmHg
	$\leq 90$ mmHg
	Decrease of $\geq 20$ mmHg from baseline and $\leq 90$ mmHg
Diastolic Blood Pressure (DBP) – Seated (mmHg)	Increase of $\geq 15$ mmHg from baseline and $\geq 105$ mmHg
	$\leq 50$ mmHg
Pulse – Seated (beats/min)	Increase of $\geq 15$ beats/min from baseline and $> 120$ beats/min
	Decrease of $\geq 15$ beats/min from baseline and $\leq 50$ beats/min
Temperature	Increase of $\geq 2.0^{\circ}\text{C}$ from baseline and $\geq 38.0^{\circ}\text{C}$
	Decrease of $\geq 2.0^{\circ}\text{C}$ from baseline and $\leq 36.0^{\circ}\text{C}$
Weight	Decrease of $\geq 7\%$ from baseline
	Decrease of $\geq 10\%$ from baseline
	Increase of $\geq 7\%$ from baseline Increase of $\geq 10\%$ from baseline

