7.1.3.2 Serotonin Syndrome (Toxicity)

Subjects are to be monitored for signs and symptoms indicative of potential serotonin toxicity, especially when initiating LMTM in this study or any medication with serotonergic potential. At each post-Baseline visit, subjects are to be evaluated by a medically qualified person by targeted physical and neurological examination and measurement of temperature, respiratory rate, blood pressure, and pulse. Results of the MMSE should also be taken into consideration. The evaluation should focus on detecting

signs and symptoms of serotonin syndrome (or serotonin toxicity) that include mental changes (confusion, hyperactivity, memory problems not attributed to underlying condition), muscle twitching, excessive sweating, shivering or shaking, diarrhea, trouble with coordination, and/or fever. A further guide is provided below.

Table 7-1 Overview of Monitoring and Management of Serotonin Syndrome (Toxicity)

Signs and Symptoms of Serotonin Toxicity	Monitoring at Each Clinic Visit	Action

Any one of the following:
 
Autonomic findings (temperature ≥ 38 °C, diaphoresis, shivering, tachypnea/dyspnea, diarrhea, hypertension or hypotension)
 
Neuromuscular changes (tremor; hyperreflexia; spontaneous, inducible, or ocular clonus; muscle rigidity¹; hypertonia; dizziness; incoordination; or mydriasis)
 
Other central nervous system changes (agitation/akathisia, elevated mood, insomnia)
	Oral (sublingual) temperature ²	
Discontinue study drug
 
Appropriate medical management to be undertaken
 
Report to Medical Monitor as AESI

	Seated blood pressure and pulse	
	Targeted PE and neurological examination, focused on the following: deep-tendon reflexes, clonus, and muscle rigidity; size and reactivity of pupils; dryness of oral mucosa; intensity of bowel sounds; skin color; and presence or absence of diaphoresis	
	MMSE (Baseline ³ , Weeks 26, 52, at the 4-week follow-up visit, and as needed to respond to changes)	

¹ Muscle rigidity can overwhelm other neuromuscular findings and mask the diagnosis

² Oral (sublingual) temperature measurements are preferable; aural temperature is an acceptable alternative (use of alternate measurement is to be noted in the eCRF)

³ MMSE to be rated at Baseline if not available from within the prior 42 days in the previous study of participation

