7.4.2 Temperature and Respiratory Rate

Temperature and respiratory rate will be measured for evaluation in the assessment for signs and symptoms indicative of potential serotonin toxicity. Oral (sublingual) temperature measurements are preferable; aural temperature is an acceptable alternative (this alternate means of measuring temperature is to be recorded in the eCRF).

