9.6.3 Vital Signs and Weight

Blood pressure, pulse, temperature, respiratory rate, and weight will be summarized for each target visit using descriptive statistics for both the original values and the change from Baseline.

Potentially clinically significant vital sign changes will be defined, and the number and percent of subjects meeting these criteria will be summarized.

Listings of vital sign measurements will be presented. Listings will flag results that meet criteria as being potentially clinically significant. Separate listings for each vital sign parameter will show results that meet criteria for being potentially clinically significant. In addition, for subjects who have one or more result that meets criteria, all corresponding vital sign results will be displayed.

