### 7.3 Vital Signs

Vital sign measurements will be summarized descriptively by target visit using the visit windows defined in [Appendix A](#) and the last available on-treatment visit; baseline will be the last non-missing value prior to the first dose of study drug. The baseline data may come from the prior study, if not repeated in 020. Vital signs include seated blood pressure and pulse, temperature, respiratory rate, and body weight. Change from baseline will also be calculated and summarized. If a subject has multiple values within a visit window, the “worst” value as defined in [Appendix D](#) will be used for that visit window summary.

Potentially clinically significant vital sign changes are defined for selected parameters in [Appendix C](#). When there are thresholds provided for low and high values, they will be handled separately. Summaries will include the number and percent of subjects with treatment-emergent PCS values, restricted to those subjects in whom the values represent a post-baseline worsening (PCST). A PCST is defined as any PCS event that happened at any post-baseline visit and has a value more out of range than the value for a particular parameter at baseline (see [Appendix D](#) for directionality of worsening).

Listings of vital sign measurements including height at Screening will be presented. Listings will flag results that meet criteria as being PCS (whether or not a treatment emergent worsening).

Separate listings for each vital sign parameter will include only subjects with study-emergent PCS values and, for these subjects, all corresponding vital sign results will be provided.

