**Table 14.3.4.1.3.1**  
**Incidence of Potentially Clinically Significant Vital Sign Results**  
**Safety Population**

Any Post-Baseline Clinically Significant Abnormalities?	Potentially Clinically Significant Criteria	Target Visit	AD (N= )	bvFTD (N= )	All Subjects (N= )
Systolic Blood Pressure	Criteria	Baseline	n (%)	n (%)	n (%)
		Any Post-Baseline Visit	n (%)	n (%)	n (%)
		Day 1 Post-Dose	n (%)	n (%)	n (%)
		Week 2	n (%)	n (%)	n (%)
Diastolic Blood Pressure	Criteria	Baseline	n (%)	n (%)	n (%)
		Any Post-Baseline Visit	n (%)	n (%)	n (%)
		Day 1 Post-Dose	n (%)	n (%)	n (%)
		Week 2	n (%)	n (%)	n (%)

path\t\_program.sas date time

*Programming note: Table will include all parameters ( systolic BP (mmHg), diastolic BP (mmHg), pulse (bpm), temperature (°C), and weight (kg)) with defined potentially clinically significant ranges at each post-Baseline visit. Table will include all target visits and Last Available On-Treatment Value. Please see Appendix A for target visits and visit windows*

*Programming Note: Repeat table for Table 14.3.4.1.3.2 Incidence of Potentially Clinically Significant Vital Sign Results – Non-AChEI/Memantine Users (Safety Population)*

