**Table 14.3.4.4.1**  
**Serotonin Toxicity (Syndrome) Assessment by Visit**  
**Safety Population**

	Time point	AD (N= )	bvFTD (N= )	All Subjects (N= )
Sign or Symptom of Serotonin Toxicity (Syndrome) Exhibited 	Baseline	(n= ) n (%)	(n= ) n (%)	(n= ) n (%)
	Week 2	(n= ) n (%)	(n= ) n (%)	(n= ) n (%)
	...			

Note: Baseline is defined as the last non-missing value prior to first dose of study drug.

 Subjects are counted if they answered “yes” to any of the signs or symptoms on the Serotonin Toxicity (Syndrome) Assessment form.

path\t\_program.sas date time

*Programming note: Table will include all target visits and Last Available On-Treatment Value. Please see Appendix A for target visits and visit windows.*

*Programming Note: Repeat table for Table 14.3.4.4.2 Serotonin Toxicity (Syndrome) Assessment by Visit – Non-AChEI/Memantine Users (Safety Population)*

**Table 14.3.4.5.1  
Central ECG Data by Visit  
Safety Population**

ECG Parameter	Time Point	AD (N= )	bvFTD (N= )	All Subjects (N= )
Ventricular Rate (bpm)	Baseline 			
	N	n	n	n
	Mean (SD)	xx.x (xx.xx)	xx.x (xx.xx)	xx.x (xx.xx)
	Median	xx.x	xx.x	xx.x
	Min, Max	xx, xx	xx, xx	xx, xx
	Week 26			
	N	n	n	n
	Mean (SD)	xx.x (xx.xx)	xx.x (xx.xx)	xx.x (xx.xx)
	Median	xx.x	xx.x	xx.x
	Min, Max	xx, xx	xx, xx	xx, xx
	Change from Baseline to Week 26			
	N	n	n	n
	Mean (SD)	xx.x (xx.xx)	xx.x (xx.xx)	xx.x (xx.xx)
	Median	xx.x	xx.x	xx.x
	Min, Max	xx, xx	xx, xx	xx, xx
...				
PR Interval (msec)				
...				

 Baseline is defined as the mean of the last non-missing triplicate values prior to first dose of study drug.  
Note: The summaries are based on the measurements from central read (BIOCLINICA).

path\t\_program.sas date time

*Programming note: table will include all target visits and Last Available On-Treatment Value and the following ECG parameters: Ventricular Rate (beats/min), PR Interval (msec), QRS Duration (msec), QTcB Interval (msec), QTcF Interval (msec). See Appendix A for visit windows.*

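### The SAP's high-temperature criterion moves with Baseline, so a subject can reach the protocol's 38 °C serotonin-toxicity sign without being counted in the PCS vital-sign table, and no table gives the number at 38 °C or above

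*SAP*

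**What the plan says.** SAP Appendix C has one criterion for high temperature, "Increase of $\geq 2.0^{\circ}\text{C}$ from baseline and $\geq 38.0^{\circ}\text{C", and one for low temperature, "Decrease of $\geq 2.0^{\circ}\text{C}$ from baseline and $\leq 36.0^{\circ}\text{C". Both conditions must hold in each case. There is no row for an absolute level alone.

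SAP 7.3 limits the PCS counts further: they are "restricted to those subjects in whom the values represent a post-baseline worsening (PCST". Table 14.3.4.1.3.1 covers the parameters "with defined potentially clinically significant ranges at each post-Baseline visit", so what it counts is fixed by Appendix C. The PCS flags and selections in the vital-sign listings follow the same criteria.

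On the protocol side, Table 7-1 in Section 7.1.3.2 lists the signs of serotonin toxicity, any one of which qualifies. The first group reads "Autonomic findings (temperature ≥ 38 °C, diaphoresis, shivering, tachypnea/dyspnea, diarrhea, hypertension or hypotension". Temperature is the only sign in that table with a numeric threshold, and it carries no condition on change from Baseline. Section 7.4.2 gives the reason for the measurement: "Temperature and respiratory rate will be measured for evaluation in the assessment for signs and symptoms indicative of potential serotonin toxicity". Section 7.1.3 names possible serotonin syndrome as one of two adverse events of special interest (AESIs).

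**The concern.** The protocol has temperature measured in order to look for serotonin toxicity and sets a level for it. The one table that reports how many subjects had a notable temperature uses a different, usually higher level that varies from subject to subject. Its temperature rows therefore do not report how often the protocol's sign was reached.

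Long-term safety is a primary objective, and the analyses are descriptive counts. A reader who takes the high-temperature row as the frequency of fever at 38 °C would read it too low, by an amount the outputs do not reveal without a search of the raw listing.

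**Working it through.** The plan states no figure on this point, so there is nothing to reproduce. The check has three parts: the cut-off implied by Appendix C, the outputs a missed reading would still reach, and the size under stated assumptions.

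**1. The effective cut-off (no assumptions)**

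Let b be Baseline and T a later reading, in °C. Appendix C needs T ≥ 38.0 and T − b ≥ 2.0, which is the same as T ≥ max(38.0, b + 2.0).

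| Baseline b | SAP cut-off | Protocol Table 7-1 |
|---|---|---|
| 36.0 | 38.0 | 38 |
| 36.4 | 38.4 | 38 |
| 36.6 | 38.6 | 38 |
| 36.8 | 38.8 | 38 |
| 37.0 | 39.0 | 38 |

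The 38.0 condition decides only when b ≤ 36.0, and 36.0 °C is the level Appendix C itself uses in its low-temperature criterion. For b = 36.8 and T = 38.7 the rise is 38.7 − 36.8 = 1.9, which is below 2.0. The subject has reached the protocol's sign and is not PCS.

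**2. Where such a reading appears**

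- Table 14.3.4.1.3.1 (PCS incidence): not counted.
- Listings 16.2.9.1, 16.2.9.2.1 and 16.2.9.2.2: the value is in 16.2.9.1 without a PCS flag, and on its own it does not bring the subject into the other two.
- Table 14.3.4.1.1.1 (descriptive): the reading enters the mean, SD, median, range and change. Appendix D takes the highest temperature in each window. A maximum shows that someone had a fever, not how many did.
- Table 14.3.4.4.1 (serotonin assessment): "Subjects are counted if they answered “yes” to any of the signs or symptoms". Listing 16.2.9.6 shows 7 autonomic, 9 neuromuscular and 4 mental-state items, 20 in all, plus a field for additional findings. Pyrexia is one of them and the table does not separate it.
- Adverse event tables: these depend on the investigator recording an event, not on a temperature level. Under Protocol 7.1.3.2, a suspected case is recorded as serotonin toxicity in place of its separate signs.

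None of these tables gives the number of subjects at 38 °C or above.

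**3. Size (assumptions, not in the documents)**

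Assume Baseline is normal with mean m from 36.2 to 36.8 and SD s from 0.3 to 0.5. Assume readings at or above 38.0 exceed it by an exponential amount with mean μ from 0.2 to 1.0, independent of Baseline.

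Share missed at reading T = P(b > T − 2.0) = 1 − Φ((T − 2.0 − m)/s). For m = 36.6 and s = 0.4:

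- T = 38.0: 1 − Φ(−1.5) = 0.933 (0.655 to 0.996 over the grid)
- T = 38.5: 1 − Φ(−0.25) = 0.599 (0.159 to 0.841)
- T = 39.0: 1 − Φ(1.0) = 0.159 (0.004 to 0.345)

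Averaged over the exponential excess, with m = 36.6 and s = 0.4:

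| μ | 0.2 | 0.3 | 0.5 | 0.8 | 1.0 |
|---|---|---|---|---|---|
| Share missed | 0.82 | 0.75 | 0.62 | 0.48 | 0.42 |

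Over the whole grid the average runs from 0.197 (m = 36.2, s = 0.3, μ = 1.0) to 0.947 (m = 36.8, s = 0.3, μ = 0.2).

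**4. After the change**

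With an absolute row at 38.0 °C, no reading at or above 38.0 is missed because of the threshold. The rule that a value must be further out of range than Baseline still applies; it would remove only subjects already at or above 38.0 °C at Baseline.

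**The case against.** The strongest reply is that the SAP contradicts nothing. Protocol 9.6.3 says only that "Potentially clinically significant vital sign changes will be defined, and the number and percent of subjects meeting these criteria will be summarized", and a rule based on change fits that wording. Appendix C uses the same combined form for high systolic pressure, high diastolic pressure and both directions of pulse. Hypertension and tachycardia are also on the serotonin form, and they have no absolute high row either. The AESI is a clinical judgement under Protocol 7.1.3, not a temperature reading, so AESI counts do not depend on Appendix C. The readings are not lost, and no test or estimate changes.

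Most of this stands. It rules out three stronger conclusions that a reader might draw:

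- That the SAP breaches a protocol threshold. The protocol sets none for PCS vital signs.
- That these subjects are absent from every vital-sign table. They are in the descriptive table and in the listings, and a ticked fever is counted in the serotonin table.
- That AESIs are undercounted. They are recorded and tabulated by a separate route.

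The argument from consistency is weaker. Temperature is the one sign to which Table 7-1 gives a number, so the SAP has a protocol value to report against, which it lacks for pressure and pulse. Appendix C also departs from the combined form where an absolute level is of interest: low systolic pressure has a row at 90 mmHg or below beside its combined row, and low diastolic pressure has only an absolute row, at 50 mmHg or below.

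**Conclusion.** The point holds as a misalignment in tabulation. The cut-off max(38.0, Baseline + 2.0) is exact and needs no assumption. It follows that any subject with a Baseline above 36.0 °C can reach the protocol's sign uncounted in Table 14.3.4.1.3.1, and that no planned table supplies the number at 38 °C or above.

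The size is not known. It is tempting to infer that most subjects who reach 38 °C are missed. The documents do not support that, because they give neither a Baseline temperature distribution nor any fever data. Under the assumptions above the missed share is about 20% to 95%. It exceeds half at exactly 38.0 °C throughout the grid, but for all readings at or above 38.0 °C it falls below half in several settings, for instance 0.48 at m = 36.6, s = 0.4 and μ = 0.8.

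The consequence is limited to one reported safety count. No inference, AESI count or clinical rule is affected.

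**What to change.** Add temperature ≥ 38.0 °C, the protocol's own value, as a separate criterion in SAP Appendix C, and carry it into Table 14.3.4.1.3.1 and Listing 16.2.9.2.1. Keep the combined criterion as a second row, following the existing layout for low systolic pressure. Optionally, show pyrexia as its own line in Table 14.3.4.4.1.

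The cost is one criterion row on data already collected. The new row will include some fevers unrelated to the drug, so a footnote should say that it counts readings and not cases of serotonin toxicity. Keeping the combined row beside it lets the reader see both counts.
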